### 667 i Investigator only

668 The PI and the study team will be monitoring patients for any safety concerns, such as 669 SAE or UAE, in real time for the duration of the 18-week study. In addition, participants 670 will be specifically asked about any adverse events after the Fixed-Dose period via 671 REDCap. Participants will be able to get in touch with a member of the study team 24/7via phone or pager for the duration of the 18-week clinical trial. The study biostatistician 672 673 will hold the randomization codes and remain blinded to the intervention assignment. In 674 the event of an SAE or UAE in which the blind needs to be broken, the Research 675 Pharmacist will be contacted by the PI or a member of the study team. The participant 676 will receive appropriate care and will be removed from the trial. A description of the 677 event will be included in the report of adverse events for the clinical study. 678

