### The specific monitoring plan for this study is based on the potential risk of participation

and size and complexity of the planned investigation. Based on these considerations, this

- study will have a monitoring committee comprised of [name], [name], and
- 654 [name], the study biostatistician. All reports of a Serious Adverse Event (SAE) or

- 655 an Unexpected Adverse Event (UAE) will be investigated by the monitoring team and 656 reported to Washington University HRPO according to the reporting requirements. 657 658 Participants who experience serious adverse effects with gabapentin therapy will be 659 removed from the study. Participants with serious adverse effects will be instructed to 660 call 911, seek immediate medical care and discontinue all further gabapentin treatment. If 661 tolerated, all participants will complete the Titration period ( $\leq 4$  weeks), Fixed-Dose 662 period (8 weeks), and Taper-Down period (2 weeks) for maximum 14 weeks of active participation. In addition, there will be a 4-week, post-Taper completion follow-up for 663 664 maximum total of 18-week trial duration.
- 665 **3.a Medical Monitoring**
- 666

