720 721	•	Grade 1: Asymptomatic or mild symptoms; clinical or diagnostic observations only; no intervention indicated
722 723	•	Grade 2: Moderate; minimal, local or noninvasive intervention indicated; limiting age-appropriate instrumental activities of daily living (ADL)
724 725 726	•	Grade 3: Severe; or medically significant but not immediately life- threatening; hospitalization or prolongation of hospitalization indicated; disabling; limiting self-care ADL
720	•	Grade 4: Life-threatening; urgent intervention indicated.
728	•	Grade 5: Death related to an AE
729		
730	iii	Expectedness

An adverse event or suspected adverse reaction is considered "unexpected" if it is not
consistent with the risk information described in this protocol or on the informed consent
or is not listed at the specificity or severity that has been observed; or, if an investigator
brochure is not required or available, is not consistent with the risk information described

in the general investigational plan or elsewhere in the current application, as amended.

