### 814 G3 Statistical Methods

815 An intention-to-treat analysis will be used for the primary analysis of the data. All

816 participants will be examined in the groups to which they were initially assigned.

817 Standard descriptive statistics will be used to assess the demographics, clinical

818 characteristics, and olfactory test results of the study population. The difference in rate of

responders after Fixed-Dose period will estimate the effect size of the primary outcome

820 measure, and the 95% CI around that point estimate will measure precision. In each

group, the frequency and relative frequency of the participants' response to the global

rating of smell change will be reported for each Likert category. Fisher's exact test will

be used for comparing the responders' rates between the 2 groups. Histograms and

- 824 Shapiro-Wilks test will be used to test the normal distribution assumption of the
- 825 continuously measured UPSIT scores and the differences pre-post treatment in each of
- the groups. Independent samples t-test or its nonparametric equivalent Mann-Whitney U
- test will be used to compare the change in UPSIT scores between the two groups. Mixed
- 828 effects model will be used to test whether the change in UPSIT score from baseline to
- end of treatment is significantly different between 2 groups. Subjects will be treated asrandom factors, and group and time will be used as fixed factors in the model. Interaction
- of group by time will be explored. Effect sizes with 95% CIs will be reported for each
- analysis. All statistical analyses will be conducted in SPSS 28 (IBM Corp., Armonk,
- 833

NY).

834

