## 840 G5 Unblinding Procedures

841 The blind will be broken for individual participants for safety concerns. Knowledge of

- 842 the treatment received is necessary for interpreting the event, may be essential for the 843 medical management of the subject, and may provide critical safety information about
- gabapentin that could have implications for the ongoing conduct of the trial (e.g.,
- 845 monitoring, informed consent). For unblinding, the research coordinator will contact the
- research pharmacist and provide the study ID number for the participant to be unblinded.
- 847 The research pharmacist will contact the PI directly and reveal the intervention
- 848 assignment. The research coordinator will remain blinded.
- 849
- 850 H
- Data Handling and Record Keeping
- 851

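### Breaking the blind for an adverse event takes the participant out of the trial and ends outcome follow-up, which conflicts with the planned intention-to-treat analysis

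*Combined protocol and SAP*

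**What the plan says.** - **F3 3.a, Medical Monitoring (Investigator only).** The rule applies in "the event of an SAE or UAE in which the blind needs to be broken, the Research" Pharmacist being contacted. The participant "will receive appropriate care and will be removed from the trial". It does not depend on the arm revealed, and no route is given to stop drug but stay in follow-up.
- **F3 3.a, Safety and Compliance Monitoring.** The abbreviation is spelled out here: "an Unexpected Adverse Event (UAE) will be investigated by the monitoring team and" reported to the institution. A separate sentence, beginning "Participants who experience serious adverse effects with gabapentin therapy will be", takes such participants out of the study and mentions no code break.
- **F3 3.b, Expectedness.** An event is unexpected if it does not fit the described risk information, "or is not listed at the specificity or severity that has been observed". This is defined separately from the severity grades.
- **2.g.** For a drug-related serious event the order is reversed: withdrawal comes first and the code break follows. An exit interview and up to 30 days of safety follow-up are provided, but no efficacy assessment.
- **2.h.** After participation ends, only exit-interview data are added, and data already collected are left out of the analysis.
- **G3.** The primary analysis is intention-to-treat, and all "participants will be examined in the groups to which they were initially assigned".
- **G4.** Missing data are assumed to be missing at random, with no adjustment.
- **G5.** "The blind will be broken for individual participants for safety concerns". The reasons given are interpreting the event, managing the participant and learning about drug safety. Removal is not mentioned.

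**The concern.** Intention-to-treat needs an outcome, or a stated rule for its absence, for everyone randomised. Here the protocol itself ends outcome collection in some participants after randomisation because of an adverse event. They may be willing and able to complete an online survey. None of the purposes in G5 requires follow-up to stop.

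F2 states that the placebo is inert, so events that prompt a code break are unlikely to be equally common in the two arms. The loss is then related to treatment, and may be related to response, while G4 treats it as ignorable. At stake is the responder difference on the Clinical Global Impression of Improvement scale (CGI-I), the pilot's main estimate, which D3 says is meant to help launch a larger trial.

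**Working it through.** **1. How the outcome is lost.** The unblinding rule takes the person out of the trial but says nothing about later assessments. The loss follows when 2.h is applied, reading a removed participant as one whose participation has ended. A code break before the end of the Fixed-Dose period (up to week 4 + 8 = 12) means the primary CGI-I is never collected. After that survey, only the later assessment is uncollected, but 2.h would still discard the primary value already given.

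**2. Who is affected by the code break alone.** Serious adverse effects on gabapentin already lead to removal under Safety and Compliance Monitoring, and in 2.g withdrawal precedes unblinding. The code break is therefore the sole trigger mainly for non-serious unexpected events that need unblinding. The documents give no rate for these.

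**3. The plan's own figure.** G1 gives 60 enrolled (30 per arm), 33% dropout, 20 evaluable per arm, 30% placebo response and a 25-point target, so 55% on gabapentin.

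0.25 ± 1.96 × √(0.55 × 0.45/20 + 0.30 × 0.70/20) = 0.25 ± 0.296, or −4.6% to 54.6%. This matches the stated −5% to 55%.

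**4. Bias in the gabapentin rate.** Let f be the fraction removed, p the response in those kept and r the response in those removed. The full-arm rate is (1 − f)p + fr. Assumptions not in the documents: f = 1/30 to 3/30 and r = 0 to 0.30. I take p = 0.55 from G1.

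| Reading of the denominator | Bias | Smallest | Largest |
|---|---|---|---|
| Complete cases (2.h; evaluable cases in G1) | +f(p − r) | 1/30 × (0.55 − 0.30) = +0.8 points | 3/30 × (0.55 − 0) = +5.5 points |
| All in the group, as in the C3 response-rate definition, no response credited to those removed | −fr | r = 0: 0 points | 3/30 × 0.30 = −3.0 points |

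**5. Check by counts (complete cases).** Start from 11/20 against 6/20, a difference of 25 points, and remove k gabapentin participants.

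| k | All removed are non-responders | All removed are responders |
|---|---|---|
| 1 | 11/19 − 6/20 = 27.9 points | 10/19 − 6/20 = 22.6 points |
| 3 | 11/17 − 6/20 = 34.7 points | 8/17 − 6/20 = 17.1 points |

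Precision hardly changes. At fixed rates of 55% and 30%, 17 against 20 gives −6.0% to 56.0%. The issue is selection, not sample size.

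**The case against.** The strongest reply is that this is a narrow special case. Only events for which the blind needs to be broken are covered, and G5 ties code breaks to safety. A reader might infer that any unexpected event, however mild, leads to removal. The text does not say so. A non-serious event can qualify, but only if unblinding is needed.

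A second reply is that most serious cases would be lost anyway under 2.g and Safety and Compliance Monitoring, and that the data loss itself comes from 2.h. This stands: changing the unblinding sentence alone would achieve little.

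A third is that the direction of bias is open. A reader might infer that the rule inflates the gabapentin effect. The documents do not support that. Nothing in them shows that removed participants would respond less, and the C3 denominator can turn the error into an understatement.

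Finally, 5.5 points is small beside an interval of −5% to 55%, and a rating obtained after a code break may be unblinded. Both are fair. They limit the weight of the point but do not remove the conflict with G3. A flagged rating can be tested in a sensitivity analysis, whereas a missing one has no planned handling.

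**Conclusion.** The point holds in a limited form. Removal after a code break, combined with 2.h and G4, produces a protocol-imposed loss of outcome that is triggered by adverse events and conflicts with the analysis in G3. The number affected is unknown and probably small.

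On the stated assumptions, the error in the gabapentin rate runs from 3 points too low to 5.5 points too high, depending on the denominator used, against a 25-point target. The expectation of imbalance between arms rests on the inert placebo, not on event rates in the documents. It is worth correcting because the correction is cheap, but it does not undermine the trial.

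**What to change.** Reconcile 2.g, 2.h, both F3 3.a passages and G5 on outcome follow-up only. All decisions about study drug and clinical care stay as they are. State that:

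- a code break, or stopping study drug, does not by itself end outcome follow-up;
- unless consent is withdrawn, the participant is asked to complete the FixedDoseSurvey and FinalSurvey on the dates originally scheduled;
- data already collected are kept;
- the participant is analysed in the assigned group, with the code break flagged.

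Add one sensitivity analysis that counts unblinded participants as non-responders.

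The cost is protocol wording and a few more surveys. These are online but not trivial: the FixedDoseSurvey has eight components, including the smell identification test. The downside is that a few CGI-I self-ratings may be made with knowledge of treatment. The flag and the sensitivity analysis show how far the result depends on them.

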### 679 **3.b Definitions of Adverse Events**

Adverse event (AE) means any untoward medical occurrence associated with the use of a
drug in humans, whether or not considered drug related (21 CFR 312.32(a)).

682

An adverse event (also referred to as an adverse experience) can be any unfavorable and
unintended sign (e.g., an abnormal laboratory finding), symptom, or disease temporarily
associated with the use of a drug, without any judgment about causality or relationship to
the drug.

687

688 An adverse event can arise from any use of the drug (e.g., off-label use, use in 689 combination with another drug) and from any route of administration, formulation, or

- 690 dose, including an overdose.
- 691

692 Serious adverse events (SAEs) are special cases of an adverse event where adverse693 outcomes are severe. SAEs include the following events:

- 694 695
- Death of any of the participants associated with a clinical trial.
- An event which can lead to life-threatening complications or put the life of participants at risk as a result of participation in a clinical trial.

698 699	•	Events that result in such a condition where the participants may require immediate hospitalization or increase the duration of hospitalization.
700	•	Any events that lead to a permanent or temporary physical disability in the body
700	•	of the participants. Any sort of incapacity is also regarded as SAE.
702 703	•	Any events that lead to any type of congenital abnormalities. It also includes any cases of birth defects resulting from the clinical trials.
704 705 706	•	Any events where an investigator or team of investigators finds feel that it can lead to significant hazards.
707 708	Class	ification of Events
709	i	Relationship
710 711 712 713 714 715 716	relation the Al (e.g., 1 AEs, 1	E or SAE may or may not be causally related to the study intervention. A causal onship means that the intervention caused (or is reasonably likely to have caused) E. This usually implies a relationship in time between the intervention and the AE the AE occurred shortly after the participant received the intervention). For all t is the responsibility of the Principal Investigator who examines and evaluates the t to determine the relatedness of the event to the study intervention.
717	ii	Severity
718 719	Sever judgm	ity refers to the intensity of a specific event and is a matter of individual clinical ent.
720 721	•	Grade 1: Asymptomatic or mild symptoms; clinical or diagnostic observations only; no intervention indicated
722 723	•	Grade 2: Moderate; minimal, local or noninvasive intervention indicated; limiting age-appropriate instrumental activities of daily living (ADL)
724 725 726	•	Grade 3: Severe; or medically significant but not immediately life- threatening; hospitalization or prolongation of hospitalization indicated; disabling; limiting self-care ADL
720	•	Grade 4: Life-threatening; urgent intervention indicated.
728	•	Grade 5: Death related to an AE
729		
730	iii	Expectedness

An adverse event or suspected adverse reaction is considered "unexpected" if it is not
consistent with the risk information described in this protocol or on the informed consent
or is not listed at the specificity or severity that has been observed; or, if an investigator
brochure is not required or available, is not consistent with the risk information described

in the general investigational plan or elsewhere in the current application, as amended.

### 737 **3.c Data Collection Procedures for Adverse Events**

- All adverse events and suspected adverse reactions are collected from 'source
- documentation' and the research coordinator will abstract the events. Documentation can

- be within Washington University EPIC medical records, but at times the research
- coordinator will also need to have the subject or family send outside source
- 742 documentation.
- 743

## 744 **3.d Reporting Procedures**

- The Principal Investigator (PI) will be responsible for ensuring participants' safety on a
  daily basis and for reporting Serious Adverse Events and Unanticipated Problems to the
  Institutional Review Board (IRB) as required.
- 748
- All SAEs will be reported immediately to the Principal Investigator upon identification.

### 750 **3.e** Adverse Event Reporting Period

751

All AEs and unanticipated problems will be reported to the IRB in a prompt and timely manner to protect other subjects from avoidable harm. The appropriate time frame for satisfying the requirement for prompt reporting will vary depending on the specific nature of the unanticipated problem. For this study, unanticipated problems that are serious adverse events will be reported to the IRB within 1 week of the investigator becoming aware of the event. Any other unanticipated problem will be reported to the IRB within 2 weeks of the investigator becoming aware of the problem.

759

Determining the appropriate time frame for reporting a particular unanticipated problem
 requires careful judgment by the Research Coordinator and the Principal Investigator
 knowledgeable about human subject protections. The primary consideration in making
 these judgments is the need to take timely action to prevent avoidable harms to other
 subjects.

765

## 766 F4 Study Outcome Measurements and Ascertainment

Participants will complete an assessment of blind after completion of 4 weeks of
the 8-week Fixed-Dose period using REDCap (survey titled: "Blind Assessment")

Participants will also complete the following forms using REDCap (survey titled
"FixedDoseSurvey") after completing the 8-week Fixed-Dose Period:

772 773

1.) Clinical Global Impression of Severity Scale (CGI-S).

7742.) Clinical Global Impression of Improvement Scale (CGI-I)

- 7753.) University of Pennsylvania Smell Identification Test (UPSIT)
- 4.) Olfactory Dysfunction Outcomes Rating (ODOR)
- 777 5.) *NASAL-7* 
  - 6.) Clinical Global Impression-Severity Scale for Parosmics (CGI-P)
- 779 7.) Adverse Event assessment
- 780 8.) Compliance
- 781

782	Participants will also complete the following forms using REDCap (survey titled		
783	FinalSurvey) 4 weeks after completing the Taper Period.		
784	1)	Clinical Global Impression of Severity Scale (CGI-S).	
785	2)	Clinical Global Impression of Improvement Scale (CGI-I)	
786	3)	University of Pennsylvania Smell Identification Test (UPSIT)	
787	4)	Olfactory Dysfunction Outcomes Rating (ODOR)	
788	5)	NASAL-7	
789	6)	Clinical Global Impression-Severity Scale for Parosmics (CGI-P)	
790			
791			

792 G Statistical Plan

793

### 794 G1 Sample Size Determination and Power

795 To date there have been no studies investigating efficacy of gabapentin in COVID-19 796 related olfactory dysfunction. Due to the lack of preliminary data and effect size, 797 estimates of the sample size for this study will be determined based on feasibility. For 798 this pilot study, we plan to enroll 60 subjects. The sample size of 60 subjects is feasible 799 given the incidence of COVID-19 cases in Missouri and considering a conservative 800 estimate of a 10% rate of permanent olfactory dysfunction among those (~50%) who 801 experience olfactory dysfunction as one of the presenting symptoms. Using a 33% drop 802 out rate, we estimate that the sample size of 60 subjects randomized in a balanced way 803 between the two treatment groups will provide us with 40 evaluable cases. A previous 804 study exploring a different treatment for COVID-19 related anosmia in our lab showed 805 that 30% of the participants randomized to placebo reported improvement at the end of 806 the trial as compared to baseline. We aim to observe a 25% difference in the response 807 rate between gabapentin and placebo groups. Assuming that this will be the response rate 808 in the placebo group of our trial, the sample size of 20 subjects per group will provide us 809 with a 95% Confidence Interval -5% to 55% around the desired proportion difference of 810 25% between gabapentin and placebo groups.

811

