#### 481 3.c Method for Assigning Subjects to Treatment Groups

482 The participants will be divided using permuted block randomization in a 1:1 allocation

- 483 between two arms: the oral gabapentin group and the oral lactose placebo group with 20
- 484 persons in each group.

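### Section 3.c puts 20 people in each arm although G1 randomises 60, and the only precision figure (-5% to 55%) is for 20 evaluable per arm, not for the intention-to-treat analysis named as primary

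*Combined protocol and SAP*

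**What the plan says.** **Numbers.** G1 says: "this pilot study, we plan to enroll 60 subjects". It then applies the attrition allowance ("Using a 33% drop" out rate) and concludes that balanced randomisation "between the two treatment groups will provide us with 40 evaluable cases". The placebo rate comes from an earlier trial in the same laboratory, which found "that 30% of the participants randomized to placebo reported improvement at the end of" follow-up. The target is given as "We aim to observe a 25% difference in the response" rate. The resulting precision, "with a 95% Confidence Interval -5% to 55% around the desired proportion difference of" 25%, is stated for 20 per group.

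Section 3.c, on assigning subjects to treatment, describes 1:1 permuted-block allocation "between two arms: the oral gabapentin group and the oral lactose placebo group with 20" persons in each.

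**Analysis set.** Four sections bear on who is counted.

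- G3: "An intention-to-treat analysis will be used for the primary analysis of the data. All" participants are analysed in the arm first assigned.
- C3 (Primary Outcome): the response rate is responders over the number of participants in the group, with no restriction to completers.
- 2.h: data gathered before a participant withdrew are left out of the analysis.
- G4: missing data are assumed to be missing at random, and no computational adjustment is made.

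**The concern.** G1 bases the sample size on feasibility and gives no power. The interval is therefore the only quantitative statement of what the pilot can deliver, and the plan says the results are meant to help start a larger trial. A reader needs to know how many people are randomised and which set of people the interval describes.

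The documents give two answers to each question. The number randomised per arm is 30 by G1 and 20 by 3.c. The set analysed is everyone assigned by G3 and C3, but only those with outcomes by 2.h and G4. With a third of participants expected to be lost, the second question affects both the width of the interval and, depending on the missing-outcome rule, the difference it is centred on.

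**Working it through.** **Inputs.** From G1: 60 enrolled, 33% dropout, 40 evaluable, placebo response 30%, target difference 25 points (so gabapentin 55%), two-sided 95% level. From 3.c: 20 per group. An equal split of dropouts between arms is assumed.

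**Formula.** Unpooled Wald interval: d ± 1.96 × √[p₁(1−p₁)/n + p₂(1−p₂)/n], with n per arm.

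**Step 1: attrition.** 60 × (1 − 0.33) = 40.2, so about 40 evaluable, or 20 per arm. G1 is internally consistent.

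**Step 2: the plan's own interval.** 0.30 × 0.70 + 0.55 × 0.45 = 0.21 + 0.2475 = 0.4575. With n = 20, SE = √(0.4575/20) = 0.151 and the half-width is 29.6 points. The interval is -4.6% to 54.6%, which rounds to the stated -5% to 55%. The figure is reproduced.

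**Step 3: section 3.c taken literally.** 20 × 0.67 = 13.4, so about 13 evaluable per arm. √(0.4575/13) = 0.188, half-width 36.8 points, interval -11.8% to 61.8%.

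**Step 4: 30 per arm, outcomes obtained for everyone at 30% versus 55%.** √(0.4575/30) = 0.1235, half-width 24.2 points, interval 0.8% to 49.2%.

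**Step 5: 30 per arm, 10 dropouts per arm counted as non-responders (an assumption, not in the plan).** Responders among the 20 evaluable are 0.30 × 20 = 6 on placebo and 0.55 × 20 = 11 on gabapentin. The rates become 6/30 = 20.0% and 11/30 = 36.7%, a difference of 16.7 points. √[(0.20 × 0.80 + 0.367 × 0.633)/30] = 0.114, half-width 22.4 points, interval -5.7% to 39.1%.

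| Reading | n per arm | Difference (points) | 95% interval |
|---|---|---|---|
| G1, evaluable cases | 20 | 25 | -4.6% to 54.6% |
| 3.c literal, after 33% dropout | 13 | 25 | -11.8% to 61.8% |
| All assigned, complete outcomes | 30 | 25 | 0.8% to 49.2% |
| All assigned, dropouts as non-responders (assumed) | 30 | 16.7 | -5.7% to 39.1% |

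**Sensitivity.** If the 40 evaluable split 24 and 16 (placebo and gabapentin), the first row becomes -5.5% to 55.5%, so modest imbalance changes little. If dropouts in both arms respond at 15% or 30% (also assumptions), the difference stays at 16.7 points, with -6.8% to 40.2% and -7.6% to 40.9% respectively.

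**The case against.** The strongest reply is that G1 contains no error. The interval is right, its basis of 20 per group is stated openly, and quoting precision for the expected evaluable cases is common practice. If all 60 gave outcomes at the planned rates, the stated interval would merely be conservative. Because the sample size rests on feasibility, a different interval would not change the 60. All of this stands.

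A reader might infer more strongly that the interval does not describe the analysis that will be run. The documents do not support that. Applied literally, 2.h and G4 give an observed-case analysis of about 40 people, which is the set behind -5% to 55%. Analysing people in their assigned arm settles where they are counted, but does not supply a CGI-I rating for someone who has none.

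A reader might also infer that the expected effect falls by a third. That follows only if missing outcomes are handled as in step 5 or its variants, and no section adopts such a rule. Moreover, the 30% placebo rate is described as a share of those randomised in the earlier trial. If it already had dropouts in its denominator, reducing it to 20% would discount them twice.

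The reply does not remove the conflict between 3.c and G1, or the conflict between the two pairs of rules on who is analysed.

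**Conclusion.** Two contradictions hold.

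First, 20 per group in 3.c cannot be the number randomised if G1's 60 is right. It looks like the evaluable target placed in the allocation section. Taken as written, it would leave about 13 evaluable per arm and widen the half-width from about 30 to about 37 points. This assumes that the same 33% dropout applies.

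Second, the only precision figure is a completer figure, while G3 and C3 name an intention-to-treat comparison over everyone in each group. For 30 per arm the half-width is about 22 to 24 points under steps 4 and 5, and the lower limit lies on either side of zero depending on the missing-outcome rule.

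There is no single correct replacement interval until that rule is chosen. The figures assume the response rates in G1, equal dropout and the Wald method that reproduces the plan's own figure. The 16.7-point scenario is an illustration, not a forecast. This is an inconsistency about group size and analysis set, not a miscalculation, and it should be corrected.

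**What to change.** 1. In 3.c, give 30 randomised per group, with about 20 per group expected to be evaluable, to agree with G1.
2. Name the primary analysis set once, and say how a participant without a CGI-I rating at the end of the Fixed-Dose period is classified. Bring C3, 2.h, G3 and G4 into line with that choice. If the set is to be those with observed outcomes, the intention-to-treat label and the C3 denominator must change. If it is to be everyone assigned, the exclusion in 2.h and the silence in G4 must change.
3. In G1, label -5% to 55% as the precision for 20 evaluable per group and add the expected difference and interval for the intention-to-treat set under the rule chosen in item 2. With complete outcomes this is 25 points and 0.8% to 49.2%. If missing ratings were counted as non-response, it would be 16.7 points and -5.7% to 39.1%.

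The cost is a few sentences across five sections and one decision about missing outcomes, best made before unblinding. No additional participants or assessments are needed.
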